7.8. Implementation Analyses

Qualitative data from semi-structured interviews are analyzed using constant comparative methods and thematic content analysis, guided by a hybrid deductive-inductive approach informed by the Consolidated Framework for Implementation Research (CFIR). Two coders independently code transcripts using a pre-specified codebook, with discrepancies resolved by consensus. Interrater reliability is assessed using the kappa statistic, with a target of 0.80 or higher. Findings are validated through member checking with additional key decision makers.

7.9. Handling of Missing Data

Patterns of missingness in physician-level, patient-level, and hospital-level variables are described prior to analysis using a systematic audit of all key variables. Missingness proportions are reported overall and separately by treatment arm to identify any evidence of differential missingness. Variables with non-random or high ($\geq 10\%$) missingness are identified and handled on a case-by-case basis.

The likely missing data mechanism is assessed based on the overall level of missingness, its distribution across arms, and its concentration by variable type. Where missingness is low, non-differential between arms, and concentrated in self-reported variables rather than outcome or claims-derived variables, a missing at random (MAR) or missing completely at random (MCAR) mechanism is considered most plausible. A missing not at random (MNAR) mechanism cannot be formally excluded and is acknowledged as a limitation where relevant.

The ITT approach mitigates the impact of missing outcome data by including all randomized physicians who filed Medicare claims, regardless of intervention adherence. Complete case analysis is used for the primary effectiveness analysis. If missingness in key covariates is substantial ($\geq 10\%$), sensitivity analyses using multiple imputation by chained equations (MICE) will be considered as a pre-specified contingency.

7.10. Type I Error Rate

A one-sided significance level of 0.05 is used for the primary hypothesis test to boost statistical efficiency and because we prioritize identification of a positive effect of the intervention. A negative effect would produce the same outcome as a null: the decision to pause further efforts to disseminate the intervention.

Protocol deviation (Version 1.4): After database lock and prior to unmasking, the study statistician determined that a two-sided test at $\alpha = 0.05$ was more appropriate given the standard implementation of the mixed effects logistic regression framework used and CONSORT reporting requirements. This is equivalent to a one-sided threshold of $\alpha = 0.025$ and represents a more conservative standard. This deviation is disclosed in the manuscript Limitations.

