		5.2.1	Secondary outcome measure of functional independence delayed	Cost of data purchase
1.4	9/29/25	7.5	Primary analysis will not include baseline covariates or random effects for the hospital	Parsimony; model stability
		7.7	Add a complier average causal effect analysis (CACE) to per protocol analysis to test the effect of study protocol compliance	Robustness
		7.10	One-sided alpha changed to a two-sided test	Improve rigor of interpretation
DATA LOCK OCCURS – October 1, 2025				
1.5	10/3/25	5.3	Re-defined dose as game usage during each intervention period instead of based on time spent.	Improve understanding of mediation
		7.1	Remove exploratory analysis of fidelity of intervention receipt; remove mediation analysis of clinical outcomes	Inability to acquire correct statistical package on CMS Virtual Desktop; results preclude necessity

SUMMARY

Study Population: The primary study population consists of 800 board-certified emergency physicians employed at non-trauma centers in the continental US. Outcomes are assessed using Medicare claims from patients aged 65 or older treated by trial physicians during the one-year post-enrollment period.

Design: This is a Phase 3, Type 1 hybrid effectiveness-implementation randomized clinical trial in which physicians are randomized 1:1 to play *Night Shift 2024* (game-based training) or to receive usual education (control). The primary outcome is assessed using Medicare claims data collected for 13 months after the close of enrollment.

Sample Size: A total of 800 physicians (400 per arm) provides 80% power to detect a 7.4% to 10% absolute reduction in under-triage at a one-sided significance level of 0.05, assuming an intraclass correlation coefficient of 0.45 and a median of 1-2 eligible patients per physician.

TABLE OF CONTENTS

1. ABBREVIATIONS	7
2. BACKGROUND AND RATIONALE	8
3. ENROLLMENT CRITERIA	8
3.1. Physician Participants	8
3.1.1. Inclusion criteria	9
3.1.2. Exclusion criteria	9
3.2. Patient Participants	9
3.2.1. Inclusion criteria	9
3.2.2. Exclusion criteria (primary analysis)	9
3.3. Hospital Characteristics	9
3.4. Key Decision Makers	10
3.4.1. Inclusion criteria (must meet at least one of the following)	10
3.4.2. Exclusion criteria	10
4. INTERVENTIONS	10
4.1. Intervention Arm (Game-Based Training)	10
4.1.1. Dosing and administration	10
4.1.2. Measurement of fidelity of treatment delivery	11
4.1.3. Measurement of fidelity of treatment receipt	11
4.2. Control Arm (Usual Education)	11

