The primary model will the following baseline covariates: patient-level characteristics (age, sex, age-adjusted Charlson Comorbidity Index score); physician-level characteristics (sex, years of experience, number of shifts per month; and hospital-level characteristics (resource availability, bed size, teaching status). The analysis is conducted on the ITT population. A one-sided hypothesis test is used at a significance level of 0.05.

The test statistic follows a chi-square distribution with degrees of freedom equal to the number of variance parameters removed. Variance components for both random effects, including estimated variances and corresponding intraclass correlation coefficients at the physician and hospital levels will be reported. These results are interpreted as evidence of the degree of clustering of patients within physicians and physicians within hospitals, respectively, and provide empirical justification for the multilevel modeling approach used in this trial.

Protocol Deviation (Version 1.4): We decided to use unadjusted primary model with no baseline covariate adjustment and clustering only at the physician level to ensure transparency and to maximize chances for model stability. In sensitivity analyses we did test the effect of

clustering at the hospital level (patients nested within patients within hospitals), and then assessed variance to determine whether to retain the clustering or not.

Protocol Deviation (Version 1.5): We had pre-specified the use of a one-sided significance test of 0.05. However, during analysis, consistent with the CONSORT guidelines, we used a two-sided test, which corresponds to a one-sided test of 0.025. We disclose this deviation in the Methods of the paper.

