7.7.4. Mediation of the game's effect on clinical outcomes

We test whether the game exerts its effect on clinical outcomes through the pathway of under-triage, using a causal mediation analysis as above. Again, we decompose the effect of the game on clinical outcomes into direct and indirect effects representing pathways independent of and operating through the mediator.

Protocol Deviation (Version 1.5): We eliminated this mediation analysis testing once we recognized that the game did not influence clinical outcomes.

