10. APPENDIX

10.1. Comparison of analytic elements across study documents.

Domain	DSMB protocol	Manuscript	Status	Rationale
Core Design Elements				
Primary outcome	Under-triage of severely injured patients (i.e., those with an ISS ≥ 16)	Under-triage of severely injured patients (i.e., those with an ISS ≥ 16)	Consistent	No change
Secondary outcomes	Over-triage; Mortality/readmission; Functional dependence*	Over-triage Mortality/readmission	*Deferred	SNF claims not available
Follow up	01/01–12/31/2024 (V1) 365 days (V1.2)	365 days	Consistent	No change
Analysis population	Intention-to-treat	Intention-to-treat	Consistent	No change
Unit of analysis	Patient	Patient	Consistent	No change
Statistical model	Mixed-effects logistic regression	Mixed-effects logistic regression	Consistent	No Change
Clustering	Physician-level and hospital-level random effects (V 1) Physician (V 1.4)	Physician-level	Consistent	No change
Covariate adjustment	Patient, physician, hospital (V1) None (V1.4)	None	Consistent	No change
Repeated measures	Sensitivity analysis	Sensitivity analysis	Consistent	N/A
Power calculation	Detailed	Overview only	Consistent	N/A
Alpha level	0.05	0.025	Deviation	Discussed in the methods
Sidedness of tests	One-sided	Two-sided	Deviation	Discussed in Methods
Multiplicity control	Not done	Not done	Consistent	N/A
Reporting and Secondary Analyses				
Effect modification	Sex, race, attitudes to video games	Sex, race, attitudes to video	Consistent	Simplify manuscript
Mediation analysis	Dose, game use–time to treatment of patients	Dose, game use–time to treatment of patients	Consistent	No change
Mediation analysis	Fidelity of intervention receipt	Not done	Not performed	Statistical package not available
Mediation analysis	Effect of under-triage on clinical outcomes	Not done	Not performed	No difference in clinical outcomes

Domain	DSMB protocol	Manuscript	Status	Rationale
Sensitivity analyses	None (version 1) Multiple (version 1.7)	Multiple	Expanded	Increase rigor

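### The SAP's final primary rule is two-sided 0.05, but its record of when that replaced one-sided 0.05 contradicts itself, an Appendix cell misstates the threshold, and the 80% power claim was not updated

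*SAP*

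**What the plan says.** **Threshold.** The main text of SAP 7.5 reads "A one-sided hypothesis test is used at a significance level of 0.05", and 7.10 opens with "A one-sided significance level of 0.05 is used for the primary hypothesis test". The Summary and 7.2 use the same one-sided level for the sample size. Deviation notes in 7.5 and 7.10 then replace it. The 7.10 note gives the new rule as two-sided 0.05 and equates it to one-sided 0.025. Appendix 10.1 has the row "Alpha level 0.05 0.025 Deviation", where the second figure is the manuscript's, and its next row gives the manuscript's test as two-sided.

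**Timing.**
- The revision table, under Version 1.4 (29 September 2025), has "One-sided alpha changed to a two-sided test". Below that entry stands "DATA LOCK OCCURS – October 1, 2025".
- The 7.10 note carries the Version 1.4 label but begins "After database lock and prior to unmasking, the study statistician determined that a two-sided test".
- The 7.5 note carries the Version 1.5 label (3 October 2025) and says "However, during analysis, consistent with the CONSORT guidelines, we used a two-sided test, which corresponds to a one-sided test of 0.025".
- Appendix 10.1 shows the DSMB protocol as one-sided 0.05 with no Version 1.4 entry, although it marks Version 1.4 changes for clustering and covariates.

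**Disclosure.** Section 7.5 and the Appendix say the deviation is reported in the manuscript's Methods; 7.10 says Limitations.

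**The concern.** A change to the primary decision rule close to database lock is credible only as far as its date can be verified. This SAP was reconstructed on 6 March 2026, after the trial ended, so its version record is the only support that the documents offer for that date, and the record disagrees with itself. Version 1.5 also contains decisions informed by results: 7.7.4 drops a mediation analysis "once we recognized that the game did not influence clinical outcomes". If the test was changed in Version 1.5, as 7.5 says, it shares a version with those decisions; if in Version 1.4, it does not.

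The rule also settles how some results are read. A favourable two-sided p between 0.05 and 0.10 succeeds under the originally specified one-sided rule and fails under the final one. A p between 0.025 and 0.05 succeeds under 7.10 and would fail if the two Appendix rows were joined literally. Separately, the power statement still describes a test that is no longer the primary one.

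**Working it through.** **1. Dates side by side**

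| Place in SAP | Version label | Stated time |
|---|---|---|
| Revision table | 1.4 (29 Sept 2025) | above the 1 Oct lock line |
| 7.10 deviation note | 1.4 | after lock, before unmasking |
| 7.5 deviation note | 1.5 (3 Oct 2025) | during analysis |
| Appendix 10.1 | none shown for the DSMB protocol | not stated |

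A change recorded on 29 September cannot have been decided after a lock on 1 October, and one change cannot belong to both versions. The words in 7.5 and 7.10 can be reconciled, because 6.2 keeps analysts masked throughout the analysis; their version labels cannot.

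**2. Critical values**

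- One-sided 0.05: z = 1.645.
- Two-sided 0.05: z = 1.960. One-sided 0.025 also gives 1.960, so the SAP's equivalence is exact.
- Two-sided 0.025 (Appendix rows joined literally): z = 2.241.

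**3. The plan's own figure**

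Inputs from 7.2: 400 physicians per arm, at least 75% contributing (300), a median of 1 to 2 patients each (m), ICC 0.45, 80% power, one-sided 0.05. Section 7.2 gives no control rate, so 50% to 60% is assumed here.

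- Effective n per arm = physicians × m / (1 + (m − 1) × 0.45).
- 300 physicians, m = 1: n = 300. 400 physicians, m = 2: n = 800/1.45 = 551.7.
- Power = Φ[(Δ√n − z√(2p̄q̄)) / √(p₁q₁ + p₂q₂)], solved for Δ at 80%.
- At a 50% control rate: Δ = 10.08 points (n = 300) and 7.46 points (n = 551.7). At 60%: 10.08 and 7.42.

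This matches 7.4 to 10, though its two ends use different physician counts. The match alone does not identify the test: a 78% control rate with z = 1.960 gives 7.36 and 10.14. What ties the range to one-sided 0.05 is the SAP's explicit statement in the Summary and 7.2.

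**4. Effect of the change**

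This step needs no control rate. At a difference with 80% power under one-sided 0.05, the expected z is 1.645 + 0.842 = 2.486.

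- Two-sided 0.05: power = Φ(2.486 − 1.960) = 0.70.
- Detectable-difference ratio = (1.960 + 0.842)/2.486 = 1.127, so 7.4 × 1.127 = 8.3 and 10 × 1.127 = 11.3 points.
- Sample-size ratio for the original differences = 1.127² = 1.27.
- Two-sided 0.025, literal Appendix only: power = Φ(2.486 − 2.241) = 0.60.

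**5. Direction**

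Every favourable result with two-sided p below 0.05 has one-sided p below 0.025, and so also passes one-sided 0.05. The new rule cannot turn a failure for benefit into a success.

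**The case against.** The strongest defence is that the rule is clear enough. The SAP keeps the superseded text, follows it with labelled deviation notes, and states two-sided 0.05 in 7.10. One-sided 0.05 is therefore disclosed history, not a live competitor. Both notes explain 0.025 as the one-sided equivalent, which is very probably what the Appendix cell means; the Appendix also describes the manuscript and does not set the rule. All of that stands. A reader might infer that three thresholds are in force, but the documents do not support this: two-sided 0.025 arises only from joining two rows, so the 60% power figure belongs to a misreading. The cell still needs a label, because it does not say which scale it uses.

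A reader might also infer that the test was changed after the results were seen. The documents do not show that. Section 7.7.4 concerns clinical outcomes, not under-triage; two of the three dated accounts assign the change to Version 1.4; and analysis can begin while analysts are masked. The change is also stricter for benefit, so the usual worry about a late threshold change, manufacturing a success, does not apply.

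A clerical cause is plausible. The gap between Version 1.4 and lock is two days, and the log has another slip: Version 1.3 is dated 2024 on the title page and 2025 in the revision table. That slip also means the log cannot settle the question by itself.

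**Conclusion.** The point holds as a fault in the record and in the power statement. The final primary rule is two-sided 0.05. The SAP contradicts itself on whether the decision came before or after lock and on whether it belongs to Version 1.4 or 1.5, so it does not establish when the decision was made. Type I error for benefit is not inflated, and there is no evidence that the change followed sight of the primary result.

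The stated 80% power applies to the one-sided design. For the same differences it is about 70% under the rule now in force. This rests on the normal approximation and on taking the SAP's 80% at 7.4 to 10 points as given; it does not depend on the assumed control rate. The correction is needed because it concerns the rule that decides the primary result and whether that rule must be called post hoc.

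**What to change.** 1. In the 7.5 and 7.10 deviation notes and in Appendix 10.1, state alpha and sidedness together: two-sided 0.05, equivalent to one-sided 0.025. Correct the Appendix alpha cell to 0.05, or label 0.025 as the one-sided equivalent.
2. Give one dated statement of when the decision was made relative to lock and unmasking, supported by the DSMB protocol version or other contemporaneous evidence. Use it identically in the revision table, 7.5, 7.10 and the Appendix, and align the place of disclosure. If the change cannot be shown to predate unmasking, label it post hoc.
3. Keep one-sided 0.05 in the Summary and 7.2 as the original design basis. Substituting two-sided 0.05 there alone would make the 80% claim false. Add that power under the two-sided test is about 70% for the same differences, or that the difference detectable with 80% power is about 8.3 to 11.3 points.
4. Report the originally specified one-sided p-value beside the two-sided result.

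The cost is wording, retrieval of the dated evidence, one extra p-value and a less favourable power figure.

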8. ETHICAL CONSIDERATIONS

8.1. Regulatory and Ethical Oversight

This trial is conducted in accordance with the International Council on Harmonization Good Clinical Practice (ICH GCP) guidelines, applicable US federal regulations (45 CFR Part 46, 21 CFR Parts 50 and 56), and NIH requirements for the conduct of clinical trials. The protocol, informed consent forms, and all recruitment materials have been reviewed and approved by the University of Pittsburgh Human Research Protection Office (HRPO). Any amendments to the protocol require HRPO review and approval prior to implementation.

8.2. Informed Consent

Digital informed consent is obtained from all physician participants and key decision makers prior to enrollment. Consent forms emphasize that participation is voluntary, that withdrawal is permitted at any time without penalty, and that study participation is not a condition of employment with the participating staffing organizations. Patient participants treated by trial physicians are not consented individually; a waiver of informed consent has been granted by the HRPO on the grounds that the research involves no more than minimal risk, could not practicably be conducted without the waiver, and will not adversely affect patient rights or welfare. A waiver of HIPAA authorization has additionally been granted for the use of Medicare claims data.

8.3. Data Safety and Monitoring Board

An independent Data and Safety Monitoring Board (DSMB) composed of experts in trauma surgery, statistics, and clinical trial conduct oversees the safety and progress of the trial. The DSMB meets at least every nine months, reviews safety and efficacy data from both arms, and provides recommendations to the NIA. DSMB members are free of conflicts of interest and independent from the study team. The DSMB operates under an approved charter established at its first organizational meeting.

8.4. Adverse Events

An adverse event (AE) is defined as any untoward or unfavorable occurrence temporally associated with study participation, whether or not considered related to the intervention. Expected AEs in this trial are limited to reports of stress experienced by physician participants, given the voluntary nature of participation and the non-clinical nature of the intervention. A serious adverse event (SAE) is defined as any AE resulting in death, life-threatening condition, hospitalization, persistent disability, or congenital anomaly. All AEs are documented using the NIA Severe Adverse Event Form and reported to the IRB within 10 days; SAEs are reported to the NIH and IRB within 48 hours of the investigator becoming aware of the event. A summary of all AEs is provided to the NIA Program Officer and the DSMB at each scheduled meeting. In the event of an AE or SAE, all trial participants are notified by email within 7 days.

8.5. Confidentiality and Data Protection

All participants are assigned unique study identifiers at enrollment. Identifying information is stored separately from research data on secure University of Pittsburgh servers and is accessible only to authorized study team members. Medicare claims data are stored on the CMS Virtual Desktop and accessed via VPN with two-factor authentication. Data are not permitted to leave the CMS servers. Upon completion of the study, de-identified primary trial data and code for cleaning the Medicare files will be transmitted to the Inter-university Consortium for Political and Social Research (ICPSR) for archiving and future use by other researchers, consistent with NIH data sharing policies.

8.6. Conflict of Interest

No members of the investigative team have a financial interest related to this research. Conflicts of interest for all study personnel are disclosed and managed in accordance with University of Pittsburgh and NIA policies. DSMB members are similarly required to disclose and manage any actual or perceived conflicts of interest prior to their appointment.

9. FUNDING

This trial is funded by the National Institute on Aging (NIA) of the National Institutes of Health (NIH) under grant number R01 AG076499, awarded to the University of Pittsburgh. The sponsor and funder had no role in the design of the statistical analysis plan. Results will be disseminated in accordance with the NIH Public Access Policy, which requires submission of peer-reviewed manuscripts to PubMed Central upon acceptance for publication. The trial is registered at ClinicalTrials.gov (NCT06063434).

10. APPENDIX

10.1. Comparison of analytic elements across study documents.

Domain	DSMB protocol	Manuscript	Status	Rationale
Core Design Elements				
Primary outcome	Under-triage of severely injured patients (i.e., those with an ISS ≥ 16)	Under-triage of severely injured patients (i.e., those with an ISS ≥ 16)	Consistent	No change
Secondary outcomes	Over-triage; Mortality/readmission; Functional dependence*	Over-triage Mortality/readmission	*Deferred	SNF claims not available
Follow up	01/01–12/31/2024 (V1) 365 days (V1.2)	365 days	Consistent	No change
Analysis population	Intention-to-treat	Intention-to-treat	Consistent	No change
Unit of analysis	Patient	Patient	Consistent	No change
Statistical model	Mixed-effects logistic regression	Mixed-effects logistic regression	Consistent	No Change
Clustering	Physician-level and hospital-level random effects (V 1) Physician (V 1.4)	Physician-level	Consistent	No change
Covariate adjustment	Patient, physician, hospital (V1) None (V1.4)	None	Consistent	No change
Repeated measures	Sensitivity analysis	Sensitivity analysis	Consistent	N/A
Power calculation	Detailed	Overview only	Consistent	N/A
Alpha level	0.05	0.025	Deviation	Discussed in the methods
Sidedness of tests	One-sided	Two-sided	Deviation	Discussed in Methods
Multiplicity control	Not done	Not done	Consistent	N/A
Reporting and Secondary Analyses				
Effect modification	Sex, race, attitudes to video games	Sex, race, attitudes to video	Consistent	Simplify manuscript
Mediation analysis	Dose, game use–time to treatment of patients	Dose, game use–time to treatment of patients	Consistent	No change
Mediation analysis	Fidelity of intervention receipt	Not done	Not performed	Statistical package not available
Mediation analysis	Effect of under-triage on clinical outcomes	Not done	Not performed	No difference in clinical outcomes

Domain	DSMB protocol	Manuscript	Status	Rationale
Sensitivity analyses	None (version 1) Multiple (version 1.7)	Multiple	Expanded	Increase rigor

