2. BACKGROUND AND RATIONALE

Trauma disproportionately affects older adults, who account for nearly half of all injury-related hospital admissions and two-thirds of in-hospital injury-related deaths in the United States. The cornerstone of trauma care is timely transfer of severely injured patients to trauma centers, where mortality is reduced by 10-25% and rates of return to independent living are substantially improved. Guidelines from the American College of Surgeons specify the injury patterns that warrant transfer. Despite four decades of quality improvement efforts, under-triage (the failure to transfer severely injured patients) remains common, affecting approximately 50% of patients at non-trauma centers overall and more than 80% of patients over the age of 65.

Physicians represent the largest identifiable source of variation in triage practices, accounting for up to 40% of the variance in transfer decisions. A critical but underappreciated driver of this variation is diagnostic error rooted in poorly calibrated clinical heuristics. Older trauma patients frequently lack the classic physiologic markers of severe injury (hypotension, tachycardia, penetrating wounds) that trigger pattern recognition in physicians trained on younger populations. Compounding this, ED physicians at non-trauma centers rarely encounter severely injured patients (approximately 1 in every 1,000 presentations), receive delayed or no feedback on their triage decisions, and are therefore unable to accumulate the experience needed to recalibrate their intuitive judgments. Existing educational interventions, including Advanced Trauma Life Support (ATLS), are designed around a rational actor model of decision making and have had limited impact on real-world triage behavior.

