5.2. Secondary Endpoints

5.2.1. Patient outcomes

- **30-day mortality and readmissions:** A composite outcome capturing death or unplanned hospital readmission within 30 days of the index visit, assessed among severely injured patients treated by trial physicians.
- **Functional dependence:** The proportion of patients with a pre-injury residence at home (identified via a 90-day lookback in claims) who are discharged to a rehabilitation facility or skilled nursing facility, used as a proxy for loss of functional independence.

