7.2. Sample Size

Based on prior studies, we assume that $\geq 75\%$ of enrolled physicians will encounter at least one eligible patient (i.e., enrolled in Medicare Fee-for-Service, severely injured, age ≥ 65 years), with a median number of patients per physician of 1-2. In this clustered randomization trial, physicians serve as the randomization unit. Based on data from a prior study, we assume an intraclass correlation coefficient (ICC) of 0.45, indicating the correlation in outcomes within the same physician. Under these assumptions, with 400 physicians per group ($N=800$), we can detect between a 7.4–10% difference in under-triage between the intervention and control groups with 80% power and a significance level of 0.05, using a one-sided hypothesis test. We have chosen a one-sided hypothesis test to boost statistical efficiency and because we prioritize identification of a positive effect of the intervention. A negative effect would produce the same outcome as a null: the decision to pause further efforts to disseminate the intervention.

The sample size estimate is conservative, as it is based on a simple comparison of proportions. The mixed-effects model used in the primary analysis is expected to yield greater effective power by accounting for additional sources of variance. Sample size calculations were performed using PASS 2023.

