7.6. Secondary Endpoint Analysis

7.6.1. Patient outcomes

The composite 30-day mortality and readmission outcome and functional dependence are each analyzed using the same GLMM framework as the primary endpoint, with the respective binary outcome as the dependent variable.

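### The SAP states that the game had no effect on clinical outcomes, but the 30-day composite is tested only for a difference and the trial was sized only for under-triage

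*SAP*

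**What the plan says.** SAP 5.2.1 defines the clinical endpoint as "A composite outcome capturing death or unplanned hospital readmission within 30 days of the index visit", among severely injured patients. Functional dependence was the other clinical endpoint, but it was not measured (SAP 5.2, deviation note), so the composite is the only one left.

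SAP 7.6.1 says that the patient outcomes "are each analyzed using the same GLMM framework as the primary endpoint". That is a test for a difference. SAP 7.2 sizes under-triage alone: "we can detect between a 7.4–10% difference in under-triage between the intervention and control groups with 80% power".

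The conclusion appears in three places, each explaining why the mediation of clinical outcomes by under-triage was dropped:
- SAP 7.7.4 says it was eliminated "once we recognized that the game did not influence clinical outcomes".
- Appendix 10.1 gives the rationale "No difference in clinical outcomes".
- The revision history, in the version 1.5 entry dated after data lock, says "results preclude necessity".

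**The concern.** These statements assert absence; they do not say that a difference was looked for and not found. A difference test can support absence only if it had good power for the effects that matter, or if its confidence interval excludes them. The plan arranges for neither.

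At stake is the Protocol's secondary hypothesis (Study Aims) that adverse patient-centered outcomes will be less frequent in the game arm. A reader of the SAP could conclude that better triage does not help injured older adults, when the design could not have shown a benefit of the size its own background implies. The same wording would also cover a harm of several points.

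**Working it through.** **Inputs from the documents**
- Contributing physicians per arm: 75% of 400 = 300 (SAP 7.2, stated as a minimum).
- Patients per physician, m: median 1 to 2, used here as if a mean (SAP 7.2).
- ICC 0.45, stated for under-triage (SAP 7.2). None is given for the composite, so ICC = 0 is also tried.
- Under-triage difference, D: 7.4 to 10 points (SAP 7.2).
- Benefit of trauma-center care, R: "mortality is reduced by 10-25" percent (SAP 2).
- Two-sided 5% test, as run for the primary endpoint (SAP 7.5 and 7.10, deviation notes).

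**Assumptions not in the documents**
- The control-arm composite rate, p, is 15 to 40%.
- R is a relative reduction.
- R applies to readmission as well as death.

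**Step 1. Reproduce the plan's own figure.** Effective patients per arm: n = 300m / (1 + (m − 1) × ICC).
- m = 1: n = 300.
- m = 2, ICC 0.45: n = 600 / 1.45 = 414.
- m = 2, ICC 0: n = 600.

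In a pooled two-proportion test, one-sided 5%, a 10-point fall from 50% with n = 300 has power 79.4%. A 7.4-point fall from 80% with n = 414 has power 80.6%. So both ends of the stated range reproduce, taking the two baselines from SAP 2 because SAP 7.2 gives none.

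**Step 2. Precision for the composite.** SE = √(2p(1 − p)/n).
- Smallest: p = 0.15, n = 600, SE = √(2 × 0.15 × 0.85 / 600) = 2.06 points.
- Largest: p = 0.40, n = 300, SE = √(2 × 0.40 × 0.60 / 300) = 4.00 points.

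The difference detectable with 80% power is (1.96 + 0.84) × SE, or 5.8 to 11.2 points. The 95% CI half-width is 1.96 × SE, or about 4.0 to 7.8 points.

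**Step 3. Effect implied by the sized under-triage difference.** d = D × R × p.
- Smallest: 0.074 × 0.10 × 0.15 = 0.11 points.
- Largest: 0.10 × 0.25 × 0.40 = 1.00 point.

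**Step 4. Power.** Power = Φ(d/SE − 1.96) + Φ(−d/SE − 1.96). For D = 10 points and R = 25%:

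| p | d (points) | n = 300 | n = 414 | n = 600 |
|---|---|---|---|---|
| 15% | 0.375 | 5.2% | 5.3% | 5.4% |
| 20% | 0.50 | 5.3% | 5.4% | 5.5% |
| 30% | 0.75 | 5.5% | 5.6% | 5.9% |
| 40% | 1.00 | 5.7% | 6.0% | 6.4% |

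Smaller D or R brings power down to 5.0%, the type I error rate.

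**Step 5. Sensitivity, pooled test**
- One-sided 5%, D = 10, R = 25%: 6.5 to 9.8%.
- All 400 physicians with two unclustered patients each (n = 800), d = 1.00, p = 40%: 6.9%.
- R = 50%, D = 10: 5.8 to 10.9%.
- The upper laboratory effect in SAP 2 (18%) taken as 18 points, R = 25%: 5.6 to 9.8%.
- R read as 25 absolute points, D = 10 (d = 2.5): 9.6 to 16.0% at p = 30 to 40%, and 12.3 to 24.2% at p = 15 to 20%.
- 18 points with 25 absolute points (d = 4.5): 20.6 to 41.3% at p = 30 to 40%, and 30.2 to 64.7% at p = 15 to 20%.

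**The case against.** Sizing a trial on its primary endpoint alone is ordinary practice, and SAP 7.2 is open about it. The disputed phrases are brief reasons for omitting a mediation analysis, not a results section. Neither document prints an estimate, p-value, interval or event rate for the composite, so that its test was non-significant is itself an inference. This stands, and it limits the point to wording and reporting. But the phrases are the only statements in the SAP about this secondary hypothesis, and they are worded as findings.

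The power figures rest on the assumptions listed. SAP 2 gives a mortality benefit without saying whether it is relative or absolute, and says nothing of readmission. Eligibility was widened to Level 3–5 centers and Medicare Advantage was dropped, so the realised size may differ from the plan either way. This too stands. The figures describe the planned design, and no reading with a 10-point shift gives power above about 24%.

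A reader might infer that about 1 point is the largest clinical effect the trial's pathway allows. The documents do not support that. The 7.4 to 10 points is a detectable difference, not a ceiling. SAP 2 cites laboratory effects of 11 to 18% and baseline under-triage above 80% in older patients, and SAP 7.7.4 itself provides for a direct effect that bypasses under-triage.

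**Conclusion.** The point holds. The absence wording in SAP 7.7.4 and Appendix 10.1 goes further than a difference test with no margin, interval criterion or power statement can. At the planned size, 80% power exists only for differences of about 6 to 11 points. The effect implied by the sized under-triage difference is about 1 point or less, with power of about 5 to 6% two-sided, or about 6 to 10% one-sided at 5% for the 10-point, 25% case. These figures assume a 15 to 40% composite rate and a relative benefit that extends to readmission. Reading the benefit as absolute points raises power for a 10-point shift only to about 10 to 16% at composite rates of 30 to 40%.

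It does not follow that the game helped patients, or that the observed result is inconclusive. That depends on an interval the documents do not show. The primary endpoint is unaffected, and whether the mediation analysis should have been dropped is a separate question.

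**What to change.** In SAP 7.6.1, report the composite as an absolute difference with its 95% CI. State that the trial was not sized for this endpoint, and give the approximate detectable difference beside the one for under-triage, with its assumptions.

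In SAP 7.7.4 and Appendix 10.1, replace the absence wording with: *no statistically significant difference was detected; the trial was not powered for this outcome*, provided that is what the test showed. Let the observed interval, not non-significance, show which benefits and harms are excluded. No new decision rule for declaring no effect is needed, and the interpretation should not be written before the interval is seen.

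The cost is wording plus one marginal contrast from a model already fitted, with no new data. The stated conclusion becomes less definite.
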